## **5.2. Study Rationale**

Aclaris has conducted three (3) Phase 2 studies to determine the dose response and dose frequency of A-101 ( $H_2O_2$ ) Topical Solution in patients with common warts. The three studies conducted are identified below and they represent data collected from 406 subjects.

- **Study A-101-WART-201:** A Randomized, Double-Blind, Vehicle-Controlled, Parallel-Group, Study of A-101 Solution in Subjects with Common Warts (n=90).
- **Study A-101-WART-202:** A Randomized, Double-Blind, Vehicle-Controlled, Parallel Group Study of A-101 Topical Solution Applied Once a Week in Subjects with Common Warts (n=157).
- **Study A-101-WART-203:** A Randomized, Double-Blind, Vehicle-Controlled, Parallel Group Study of A-101 Topical Solution Applied Twice a Week in Subjects with Common Warts (n=159).

The results from Study A-101-WART-201 evaluated two concentrations of A-101 ( $H_2O_2$ ) Topical Solution: 40% and 45% (w/w) compared with vehicle. The 45% (w/w) concentrations demonstrated clinically and statistically significant results in clearing warts while the 40% concentration had no effect when compared with vehicle. Therefore, A-101 40% topical solution was judged to be an ineffective concentration and not evaluated in further Phase 2 studies.

The results from Study A-101-WART-202, which evaluated a 45% (w/w) concentration of A-101 ( $H_2O_2$ ) Topical Solution when treating a single target wart and up to 3 additional warts showed that the 45% concentration applied once weekly resulted in a clinically and statistically significant clearing of warts at the end of the treatment period (Day 56) and at the end of a 12-week post-treatment follow-up (Day 134).

The results from Study A-101-WART-203, which evaluated a 45% concentration of A-101 ( $H_2O_2$ ) Topical Solution administered twice weekly to a single target wart and up to 5 additional warts showed that the 45% (w/w) concentrations resulted in clinically and statistically significant clearing of the target wart and all treated warts at the end of the treatment period (Day 56) and at the end of a 12-week, post-treatment follow-up (Day 134). The results from Study WART-203 were clinically and statistically significant clearance of warts at the end of the treatment period (Day 56) and at the end of a 12-week post-treatment follow-up (Day 134), with consistently earlier and stronger results than the data from Study WART-202 which incorporated a once weekly dose regimen.

A-101 ( $H_2O_2$ ) 45% (w/w) Topical Solution administered once weekly and twice weekly was well tolerated. Treatment emergent adverse events were predominantly mild and unrelated to study medication. Local Skin Reactions (LSRs) were predominantly mild and transient. The LSRs of pruritus and stinging reported by subjects, and crusting, edema, erythema, and scaling reported by the investigator following treatment generally resolved by Visit 13 (Day 134). There were no clinically significant changes during the study in laboratory evaluations or vital signs.

Aclaris Therapeutics, Inc.

Protocol Number: A-101-WART-302

Amendment 3: Version 5 14 February 2019

## **6. OBJECTIVES**

### **6.1. Study Objectives**

#### **6.1.1. Primary Objective**

The primary objective of this study is to evaluate the effectiveness of A-101 45% compared to Vehicle when applied twice weekly to common warts.

#### **6.1.2. Secondary Objectives**

The secondary objectives of this study include:

- Duration of response to A-101 45% compared to Vehicle.
- Onset of action of A-101 45% compared to Vehicle.
- Safety of A-101 45%.

## 7. STUDY DESIGN

This is a phase 3, multicenter, randomized, vehicle controlled, double blind parallel group study designed to evaluate the efficacy and safety of A-101 45% compared to Vehicle in subjects with common warts.

During the study, the investigator will identify at least 1 and up to 6 common warts to be treated twice a week for up to 8 weeks (maximum of 16 treatment applications)

Subjects will be required to complete a total of 13 study visits. The protocol defined study visits are:

- Visit 1 (Day -13 to 0) screening
- Visit 2 (Day 1)\* randomization; study medication treatment
- Visit 3 (Day 8)\* study medication treatment
- Visit 4 (Day 15)\* study medication treatment
- Visit 5 (Day 22)\* study medication treatment
- Visit 6 (Day 29)\* study medication treatment
- Visit 7 (Day 36)\* study medication treatment
- Visit 8 (Day 43)\* study medication treatment
- Visit 9 (Day 50)\* study medication treatment
- Visit 10 (Day 60) follow up evaluations, no identified Wart retreatment
- Visit 11 (Day 78) follow up evaluations, no identified Wart retreatment
- Visit 12 (Day 106) follow up evaluations, no identified Wart retreatment
- Visit 13 (Day 137) follow up evaluations, no identified Wart retreatment; end of study

\*The second weekly application will be applied by the subject/parent/legal guardian at home (Day 4, 11, 18, 25, 32, 39, 46, and 53).

Refer to [Table 2](#) for a complete list of protocol required study assessments.

### 7.1. Number of Subjects and Study Centers

Approximately 500 subjects will be randomized to one of two treatment arms at approximately 25 investigational centers in the US. Of the 500 subjects randomized, approximately 100 subjects will be between 1 and 17 years of age.

### 7.2. Duration of Study

The anticipated time for study enrollment is approximately 3 months. The duration of study participation is anticipated to be a maximum of 157 days per subject. Subjects will have a total of 13 study visits. The maximum anticipated duration for the study is approximately 10 months.

## 8. STUDY ENTRY CRITERIA

### 8.1. Inclusion Criteria

Subjects must meet all the following criteria to be considered for participation in this study.

1. Subject or legal guardian is able to comprehend and is willing to sign an informed consent/assent for participation in this study.
2. Male or female  $\geq 1$  year old.
3. Subject has a clinical diagnosis of common warts (*verruca vulgaris*).
4. Subject has at least 1 and up to 6 clearly identifiable common warts located on the trunk or extremities that meet the requirements as defined below:
  - a. Have a longest axis that is  $\geq 3$  and  $\leq 8$  mm and have a thickness of  $\leq 3$ mm
  - b. Be a discrete lesion, i.e. each wart meeting the entry criteria is clearly separated from other warts.
  - c. Be present for at least 4 weeks
  - d. Not be covered with hair which, in the investigator's opinion, would interfere with the study medication treatment or the study evaluations
  - e. Not be in an intertriginous fold
  - f. Periungual, subungual, genital, anal, mosaic, plantar, flat and filiform warts are excluded from treatment and evaluation. If a subject has these types of warts, but also has warts that meet the inclusion criteria, the subject will NOT be excluded from the study.
5. Each common wart identified for treatment must have a PWA  $\geq 2$ .
6. Subject's chemistry and complete blood count results are within normal limits. If any of the laboratory values are outside normal range, the treating investigator must assess the value(s) as NOT clinically significant and document this in the subject's medical chart in order for the subject to be eligible for randomization.
7. Subject is in good general health and free of any known disease state or physical condition which, in the investigator's opinion, might impair the evaluation of the identified common warts or which exposes the subject to an unacceptable risk by study participation.
8. Subject is willing and able to follow all study instructions and to attend all study visits.
9. Subject must be the only individual in a household participating in the study.

### 8.2. Exclusion Criteria

Subjects are excluded from this study if any of the following criteria is met:

1. Subject has clinically atypical warts.
2. Subject is immunocompromised (e.g., due to chemotherapy, systemic steroids, genetic immunodeficiency, transplant status, etc.).
3. Subject has a history of Human Immunodeficiency Virus (HIV) infection.
4. Subject has had any Human Papilloma Virus (HPV) vaccine within 6 months prior to Visit 1.
5. Subject has used any of the following intralesional therapies within the specified period prior to Visit 2:
  - Immunotherapy (e.g., *Candida* antigen, mumps antigen, *Trichophyton* antigen); 8 weeks
  - Anti-metabolite therapy (e.g., bleomycin, 5-fluorouracil); 8 weeks

6. Subject has used any of the following systemic therapies within the specified period prior to Visit 2:
  - Immunomodulatory/immunosuppressant therapy (e.g., etanercept, alefacept, infliximab); 16 weeks
  - Glucocortico-steroids (inhaled and intra-nasal steroids are permitted); 28 days
7. Subject has used any of the following topical therapies within the specified period prior to Visit 2 on, or in the proximity to any of the common warts identified for treatment, that in the investigator's opinion interferes with the study medication treatment or the study assessments:
  - LASER, light or other energy-based therapy (e.g., intense pulsed light [IPL], photodynamic therapy [PDT]); 180 days
  - Immunotherapy (e.g., imiquimod, squaric acid dibutyl ester[SADBE], etc.) 12 weeks
  - Liquid nitrogen, electrodesiccation, curettage; 60 days
  - Hydrogen peroxide; 90 days
  - Antimetabolite therapy (e.g., 5-fluorouracil); 8 weeks
  - Retinoids; 90 days
  - Over-the-counter (OTC) wart therapies and cantharidin; 28 days
8. Subject currently has or has had any of the following within the specified period prior to Visit 1 on or in the proximity to any of the common warts identified for treatment that, in the investigator's opinion, interferes with the study medication treatment or the study assessments:
  - Cutaneous malignancy; 180 days
  - Sunburn; currently
  - Pre-malignancy (e.g., actinic keratosis); currently
9. Subject has a history of sensitivity to any of the ingredients in the study medications.
10. Subject has any current skin or systemic disease (e.g., psoriasis, atopic dermatitis, eczema, sun damage), or condition (e.g., sunburn, excessive hair, open wounds) that, in the opinion of the investigator, might put the subject at undue risk by study participation or interfere with the study conduct or evaluations.
11. Participation in another therapeutic investigational drug/device trial in which administration of an investigational treatment occurred with 30 days prior to Visit 1.
12. Subject has an active malignancy.
13. Subjects is viewed by the Principal Investigator as not being able to complete the study.

### **8.3. Removal of Subjects from Study Therapy**

A subject may be removed from the study therapy for a variety of reasons, including:

- Unacceptable adverse event
- Subject unwilling or refusal to continue with the protocol defined study visits and/or consent withdrawal for study participation
- Change in compliance with an inclusion/exclusion criteria
- Use of a prohibited medication (through Visit 13)
- General or specific changes in the subject's condition that render the subject unacceptable for further treatment in this study in the judgement of the investigator.

If a subject is to be withdrawn from the study, the Aclaris Therapeutics, Inc. CRA or designee must be informed within 24 hours of the decision to remove the subject from the study.

The study may be discontinued at the discretion of Aclaris Therapeutics, Inc. Some examples of reasons for discontinuation are the occurrence of the following:

- Increased frequency, severity or duration of known AEs
- Medical, regulatory or ethical reasons affecting the continued performance of the study
- Difficulties in the recruitment of subjects

#### **8.4. Withdrawal Procedures**

If a subject withdraws from the study prior to Visit 13, the reason for and the date of withdrawal from the study must be recorded on the eCRF. If the reason for withdrawal is an adverse event or a clinically significant abnormal laboratory test result, monitoring of the subject will continue until the event has resolved or stabilized, until the patient is referred to the care of a local health care professional, or until a determination of a cause unrelated to the study drug or study procedure is made.

#### **8.5. Subject Replacement**

Subjects that are determined to be screen failures may be rescreened for the study and if determined to be eligible for the study they may be randomized using the same subject identifier. A screen failure is a subject that signs an informed consent form for participation in the study but is determined not to be eligible for the study prior to the subject being randomized to the study.

#### **8.6. Subject Identifier (SI)**

The investigator or designee will assign a unique five-digit subject identifier (SI) to each subject at Visit 1.

The SI format will be NN-NNN where the first 2 digits are the investigational center site number (using leading zeroes, as appropriate). The final 3 digits are the subject number and must be assigned in ascending numerical order, without omitting or repeating any number, starting with 001 at each investigational center. For example, the SI for the second subject that signs an informed consent at site number 04 would be 04-002.

The subject will be identified using the SI in all study documentation for the duration of the study.

Aclaris Therapeutics, Inc.

Protocol Number: A-101-WART-302

Amendment 3: Version 5 14 February 2019

## **9. STUDY PROCEDURES**

The schedule of study activities (including assessments, tests, exams, disease assessments, and study drug administration) beginning with screening and continuing through the end of study are outlined in [Table 2](#) . A written, signed informed consent form (ICF) must be obtained from each subject prior to performing any study related procedure (*e.g.*, vital signs, clinical laboratory sampling, or photography).

Aclaris Therapeutics, Inc.

Protocol Number: A-101-WART-302

Amendment 3: Version 5 14 February 2019

**Table 2: Study Procedures**

| Visit                                    | V1
Screening | V2             | V3        | V4     | V5     | V6     | V7     | V8     | V9     | V10     | V11        | V12        | V13     |
|--|-----------------|----------------|-----------|--------|--------|--------|--------|--------|--------|---------|------------|------------|---------|
| Treatment Day                     | -13 to 0        | 1              | 8         | 15     | 22     | 29     | 36     | 43     | 50     | 60      | 78         | 106        | 137     |
| Treatment Window                  | N/A             | N/A            | ±1
day | ±1 day | +4 days | ±7
days | ±7
days | +7 days |
| Study Procedures                  |                 |                |           |        |        |        |        |        |        |         |            |            |         |
| Informed Consent                         | ▲               |                |           |        |        |        |        |        |        |         |            |            |         |
| Inclusion Criteria/Exclusion Criteria    | ▲               | ▲  |           |        |        |        |        |        |        |         |            |            |         |
| Subject Identifier                       | ▲   |                |           |        |        |        |        |        |        |         |            |            |         |
| Medical history/demographics             | ▲               |                |           |        |        |        |        |        |        |         |            |            |         |
| Fitzpatrick Skin Type Assessment         | ▲   |                |           |        |        |        |        |        |        |         |            |            |         |
| Vital Signs                              | ▲   |                |           |        |        |        |        |        | ▲      |         |            |            | ▲       |
| Prior Medications/Therapies              | ▲   |                |           |        |        |        |        |        |        |         |            |            |         |
| Clinical Chemistry and CBC   | ▲               |                |           |        |        |        |        |        |        |         |            |            | ▲       |
| Common Wart Identification   | ▲               |                |           |        |        |        |        |        |        |         |            |            |         |
| Physician's Wart Assessment  | ▲               | ▲              | ▲         | ▲      | ▲      | ▲      | ▲      | ▲      | ▲      | ▲       | ▲          | ▲          | ▲       |

| Visit  | V1
Screening | V2              | V3   | V4              | V5              | V6              | V7              | V8              | V9     | V10     | V11     | V12     | V13     |
|--|-----------------|-----------------|--|-----------------|-----------------|-----------------|-----------------|-----------------|--------|---------|---------|---------|---------|
| Treatment Day                               | -13 to 0        | 1               | 8  | 15              | 22              | 29              | 36              | 43              | 50     | 60      | 78      | 106     | 137     |
| Treatment Window                            | N/A             | N/A             | ±1 day   | ±1 day          | ±1 day          | ±1 day          | ±1 day          | ±1 day          | ±1 day | +4 days | ±7 days | ±7 days | +7 days |
| Common Wart Dimensions                 | ▲               | ▲               | ▲  | ▲               | ▲               | ▲               | ▲               | ▲               | ▲      | ▲       | ▲       | ▲       | ▲       |
| Standardized Photography              | ▲               | ▲  |  | ▲               |                 | ▲               |                 | ▲               | ▲      | ▲       | ▲       | ▲       | ▲       |
| Subject Randomization                              |                 | ▲  |  |                 |                 |                 |                 |                 |        |         |         |         |         |
| Local Skin Reactions                               |                 | ▲  | ▲   | ▲  | ▲  | ▲  | ▲  | ▲  | ▲      | ▲       | ▲       | ▲       | ▲       |
| Study Medication Application          |                 | ▲               | ▲  | ▲               | ▲               | ▲               | ▲               | ▲               | ▲      |         |         |         |         |
| Study Medication Application at Home  |                 |                 | A-101 Study Medication will be applied at home on Days 4, 11, 18, 25, 32, 39, 46, 53. A window of +1 day is allowed. |                 |                 |                 |                 |                 |        |         |         |         |         |
| Subject Instructions                               | ▲               | ▲               | ▲  | ▲               | ▲               | ▲               | ▲               | ▲               | ▲      | ▲       | ▲       | ▲       | ▲       |
| Concomitant therapies                 |                 | ▲               | ▲  | ▲               | ▲               | ▲               | ▲               | ▲               | ▲      | ▲       | ▲       | ▲       | ▲       |
| Adverse Events                        |                 | ▲               | ▲  | ▲               | ▲               | ▲               | ▲               | ▲               | ▲      | ▲       | ▲       |         |         |

Subject inclusion/exclusion criteria will be re-assessed prior to randomization during Visit 2.

Investigational sites will assign a unique five-digit subject identifier to each subject at Visit 1. This subject identifier will be used in all study documentation for the duration of the study.

Each subject's skin must be assessed during Visit 1 using the Fitzpatrick Skin Type Assessment.

Aclaris Therapeutics, Inc.

Protocol Number: A-101-WART-302

Amendment 3: Version 5 14 February 2019

Vital signs [including temperature, pulse, respiratory rate, blood pressure, height and weight (Visit 1 only)] will be measured by a qualified staff member at Visit 1, Visit 9 and Visit 13.

Prior medications/therapies will be collected for a time-period of 14 days prior to Visit 2. Refer to Section [11](#) for a list of permitted and restricted concomitant medications.

A complete blood count (including hematocrit, hemoglobin, platelet count, red blood cell count and morphology, white blood cell count and differential (absolute and %) including basophils, eosinophils, lymphocytes, monocytes and neutrophils and a clinical chemistry panel including albumin, alkaline phosphatase, alanine aminotransferase (ALT), aspartate aminotransferase (AST), blood urea nitrogen (BUN), bicarbonate, calcium, chloride, creatinine, glucose, lactate dehydrogenase (LDH), phosphorus, potassium, sodium, total bilirubin, total protein, and uric acid.

The treating investigator will identify at least 1 and up to 6 common warts located on the trunk or extremities that meet the inclusion criteria outlined in Section 7.

The investigator will use the Physician Wart Assessment (PWA) scale to assess each identified common wart. The investigator must assess the identified common warts prior to application of the study medication at Visit 2-Visit 9. In order to be eligible for randomization at Visit 2, each common wart must have a PWA grade  $\geq 2$ .

The investigator will measure the dimensions (longest axis and thickness of the common wart) at Visit 1 and prior to randomization at Visit 2. In order for the subject to be randomized at Visit 2 the identified common warts must have the specific dimensions outlined in Section [12.1](#). The investigator will be required to measure the longest axis of each common wart at Visits 2-13.

At Visits 1, Visit 2, 4, 6, and 9 (prior to study medication application), and Visit 10-13, a qualified investigational center staff member will take a photograph of each identified common wart using the Aclaris supplied camera. All photographs will be sent to a central imaging laboratory.

At a sub-set of investigational sites (up to 3 sites), subjects randomized at these sites will have additional standardized photographs taken of their common warts at the following time-points: V2-10 minutes post application, 1-hour post application and 24 hours post application.

Subjects will be randomized at Visit 2 prior to application of study medication. Investigational study staff will re-confirm subject eligibility prior to randomization.

The investigator and subject will assess each identified common wart for local skin reactions associated with irritation at Visits 2-13. At Visit 2-Visit 9, the investigator and subject will assess each identified common wart for LSRs prior to the application of the study medication. Refer to Section [13.1](#) for the complete list of Local Skin Reaction signs and symptoms.

During in-office visits, subjects 18 years of age and older will apply their A-101 study medication in the presence of the treating physician or a member of the investigational study staff that has been trained on the protocol. Subjects ages 1 to 17 will have their A-101 study medication applied by a parent/legal guardian in front of the treating physician or a member of the investigational study staff during in-office visits. If the identified common wart meets the criteria

for re-treatment as defined in Section 10.6 the lesion will be re-treated at Visits 3-9. Following application of study medication, subjects must NOT wash/submerge the treated wart for at least 6 hours and they must NOT apply any topical products to the treated common warts for at least 6 hours. Parents/legal guardians of children must ensure that the child does not put the treated area in their mouth, or eyes, until completely dry after the application. If the treated area is not completely dry 10 minutes after the application, the area should be blotted dry.All subjects will receive their second weekly treatment of the A-101 study medication at home on Days 4, 11, 18, 25, 25, 32, 39, 46, 53 as determined by the PWA assessment performed during the in-office visit. Subjects ages 1 to 17 will have their A-101 study medication applied by a parent or legal guardian. All subjects will need to document the application of A-101 study medication in a subject diary. The second weekly treatment will depend on the PWA performed during the in-office visit that week. If the identified common wart meets the criteria for re-treatment during the in-office visit, then the subject/parent/guardian will perform the second weekly treatment at home.

All concomitant therapies including (topical and oral) prescription medications, over the counter medications and natural supplements and non-drug therapies including chiropractic, physical therapy, and energy-based therapy must be documented in the subject CRF. Subjects must not apply any topical products (e.g., moisturizers, sunscreen, etc.) to the identified common wart within 12 hours prior to any study visit.

The reporting period for Serious Adverse Events (SAEs) begins when the subject signs the informed consent and continues through Visit 11. Refer to Section Section 14.1.2 for instructions on the reporting of SAEs. Non-serious clinical adverse events will be collected following the application of the study medication at Visit 2 and through Visit 11. Non-serious adverse events that occur between the time of consent and study medication application will be documented as medical history. All safety reporting (AEs and SAEs) will conclude at Visit 11 (approximately 28 days after last study medication application) except for clinical adverse events related to local skin reactions.

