**Retreatment Criteria:**

At Visit 3-9, if the identified common wart has a **PWA grade of >0** then the subject will receive re-treatment with the A-101 study medication treatment. However, treatment with the A-101 study medication should not be applied if any of the following criteria apply to the identified common wart:

- The common wart has a pre-treatment LSR grade of 3 (severe) for any sign or symptom AND the grade has increased compared to the previous visit.
- The common wart is, in the investigator's opinion, not appropriate for a retreatment (the investigator must note the reason on the subject's Comments CRF page).
- The common wart, in the Investigator's opinion, cannot be visualized so the Investigator cannot assess the PWA.

If the identified common wart meets the criteria for re-treatment during the in-office visit (PWA>0), then the subject/parent/legal guardian should treat the common wart at home on the protocol defined at home treatment days (Days 4, 11, 18, 25, 32, 39, 46, 53. A window of +1 day is allowed). If the subject is unable to tolerate treatment the day of an at home treatment visit due to severe skin irritation, then the treatment should be held and the investigational site should be notified.

Subjects whose identified common wart(s) is assessed at a particular visit (V3-V9) to be a PWA=0 will not have the that common wart re-treated at that visit (or retreated at the second at home application that week).

[figure not shown]

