#### **14.1.3. Adverse Event Reporting Period**

The investigator must start reporting non-serious AEs starting with the subject’s first study medication treatment continuing until Visit 11. Non-serious adverse events that occur between the time the subject was consented and the first application of study medication will be reported as medical history.

Reporting for SAEs begins after the subject signs the informed consent and continues until Visit 11 (regardless of relationship to study medication). If a subject experiences a SAE after Visit 11 that is deemed by the investigator to be related to study medication, the investigator must report this to the Sponsor using the study specific SAE report form.

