#### 3.3.2 Adverse Events

Adverse events are coded using the MedDRA (Version 22) dictionary and are categorized by system organ class (SOC) and preferred term (PT). Only treatment emergent adverse events are included in summary tabulations (i.e. adverse events occurring on or after the first application of study medication and within 30 days following the last application of study medication). All adverse events are included in the data listings including those that are not considered treatment emergent.

To allow differentiation as to which study period an Adverse Event occurred, three categories are defined based upon onset date. Adverse Events that had onset dates prior to the first application of study medication are considered "prior". Adverse events with onset dates on or after the first application of double-blind study medication and within 30 days following the last application of study medication are considered "treatment emergent". Events with onset dates more than 30 days after the last application of study medication are considered as "post-therapy".

Frequency tabulations are presented by MedDRA SOC and preferred term, for all adverse events; study treatment-related, adverse events resulting in discontinuation of study treatment, serious adverse events and adverse events by maximum severity. Adverse events resulting in discontinuation are those with 'action taken' recorded as 'drug withdrawn'.

Treatment emergent adverse event summaries by MedDRA SOC and preferred term will also be provided according to the following subgroups:

- Age (<18, 18 to 65, and >65)
- Sex (Male, Female)
- Race (White, Non-White)

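### Minor: clinically significant Visit 13 findings and related SAEs after Visit 11 each have two reporting rules, and after a Day 53 application routine AE collection nominally stops 5 days before the SAP's 30-day window closes

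*Protocol*

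**What the plan says.** **End of reporting.** Protocol Table 2, footnote 17, repeated in the SAP's Schedule of Assessments, states that AE and SAE reporting "will conclude at Visit 11 (approximately 28 days after last study medication application) except for clinical adverse events related to local skin reactions". The AE row of Table 2 has no mark at Visits 12 and 13. Protocol 14.1.3 has non-serious AEs reported from the "first study medication treatment continuing until Visit 11". Unlike the footnote, it also requires a report of any SAE after Visit 11 that the investigator judges related.

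**Where sites are sent for SAEs.** The Protocol footnote says "Refer to Section Section 14.1.2 for instructions on the reporting of SAEs". Section 14.1.2 only defines an SAE. The reporting procedure is in 14.2.2 and is written for SAEs within the AE reporting period.

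**Last application.** Study medication is "applied at home on Days 4, 11, 18, 25, 32, 39, 46, 53. A window of +1 day is allowed". A wart graded clear at an in-office visit "will not have the that common wart re-treated at that visit (or retreated at the second at home application that week", so a subject whose warts have all cleared can have an earlier last application.

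**Laboratory and vital-sign findings.** Protocol 13.2 and 13.3 require a clinically significant abnormality found after first treatment to be reported as an AE. Neither gives an end date. Blood is drawn at Visits 1 and 13; vital signs are taken at Visits 1, 9 and 13.

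**Analysis window.** SAP 3.3.2 counts as treatment-emergent "adverse events occurring on or after the first application of study medication and within 30 days following the last application of study medication". It adds that "Only treatment emergent adverse events are included in summary tabulations". "Events with onset dates more than 30 days after the last application of study medication are considered as" post-therapy, and these appear in listings.

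**The concern.** A site with a clinically significant laboratory result at Visit 13 can follow 13.3 and open an AE record, or follow footnote 17 and 14.1.3 and treat AE reporting as closed. For laboratory data this is not a corner case, because Visit 13 is the only scheduled sample after treatment starts. Vital signs share the problem at Visit 13 but not at Visit 9, which lies inside the reporting period.

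A site that learns of a related SAE after Visit 11 finds a footnote saying reporting has ended, a section saying it must report, and a cross-reference to a section with no instructions.

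The AE tables use a 30-day window after the last application. For subjects treated to the end of the schedule, routine collection of non-serious AEs (other than those related to local skin reactions) and of SAEs not judged related nominally stops before that window closes. The footnote's 28-day figure partly hides this.

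At stake are the completeness and site-to-site consistency of AE records, not any efficacy comparison.

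**Working it through.** **Inputs.** Visit 9 is Day 50. The last scheduled home application is Day 53, or Day 54 with the +1 window. Visit 11 is Day 78 ±7 (Days 71 to 85, 15 permitted days). Visit 12 is Day 106 ±7 (Days 99 to 113). Visit 13 is Day 137 +7 (Days 137 to 144). All are from Protocol Table 2. The 30-day window is from SAP 3.3.2.

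**Reproducing the stated figure.** From Visit 9: 78 − 50 = 28, an exact match. From the Day 53 home application: 78 − 53 = 25. The stated interval therefore counts from the last in-office application, not the last scheduled one.

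**Interval to Visit 11 and shortfall against 30 days.** Interval = Visit 11 day − last application day; shortfall = 30 − interval, where positive.

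| Last application | Visit 11 on Day 78 | Range, Days 71 to 85 | Shortfall on Day 78 | Largest shortfall (Day 71) | Visit 11 days covering all 30 |
|---|---|---|---|---|---|
| Day 53 | 25 | 18 to 32 | 5 | 12 | Days 83–85 (3 of 15) |
| Day 54 | 24 | 17 to 31 | 6 | 13 | Days 84–85 (2 of 15) |
| Day 50 | 28 | 21 to 35 | 2 | 9 | Days 80–85 (6 of 15) |
| Day 46 | 32 | 25 to 39 | none | 5 | Days 76–85 (10 of 15) |
| Day 22 | 56 | 49 to 63 | none | none | all 15 |

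After a Day 53 application the window runs to 53 + 30 = Day 83, so a Day 78 Visit 11 leaves Days 79 to 83 uncollected. Even a true 28 days would be 2 short of 30. The last-column counts are calendar days in the permitted window, not probabilities of when visits occur.

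**Visit 13 against the end of reporting.** 137 − 78 = 59 days after Visit 11, range 137 − 85 = 52 to 144 − 71 = 73. After the last home application it is 137 − 54 = 83 to 144 − 53 = 91 days. An AE with onset at Visit 13 in a subject treated to the end is therefore post-therapy under SAP 3.3.2, and is listed but not tabulated.

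**Would Visit 12 cover the window?** Earliest Visit 12 after the latest home application: 99 − 54 = 45 days, which exceeds 30.

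**Rules side by side, no arithmetic.**

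- Clinically significant Visit 13 finding: 13.2 and 13.3 say report as an AE; footnote 17, the Table 2 AE row and 14.1.3 say non-serious AE reporting has ended.
- Related SAE after Visit 11: footnote 17 says reporting has concluded, with an exception only for AEs related to local skin reactions; 14.1.3 says report.

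**The case against.** The strongest reply is that the 30-day rule sorts recorded AEs by onset date and does not promise 30 days of observation. That is correct. A reader might infer that the AE tables will misclassify events; the documents do not support this, since every recorded AE falls in the right category. What remains is that the tables will carry a window that routine collection does not fully cover for some subjects, and nothing tells the reader so.

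Next, the footnote says approximately, and a 3-day difference is smaller than the ±7-day visit window. The 12- and 13-day shortfalls need Visit 11 on its first permitted day. That also stands, and it limits the weight of the point. A reader might infer that every subject is followed for less than 30 days. The retreatment rule and the late end of the Visit 11 window show otherwise.

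The loss is small. AEs related to local skin reactions are exempt from the cut-off, the reactions are assessed through Visit 13, and related SAEs stay reportable under 14.1.3. It would overreach to say that Visit 13 safety data are lost: laboratory and vital-sign values reach their own summaries under Protocol 15.4 and SAP 3.3.4 and 3.3.5, whether or not an AE is recorded.

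On Visit 13 findings, 13.2 and 13.3 could be read as specific rules that override a general cut-off, or footnote 17 could be read as limiting only clinical AEs. Either is possible, but neither is stated. The footnote's last sentence covers all safety reporting, and 14.1.3 has no such qualifier. Section 14.2.1 does not settle it: AEs are elicited at each visit after enrollment, but a record is required only for those noted within the reporting period. That sites will in fact differ is an inference, since CRF instructions are not in the documents.

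On late related SAEs, 14.1.3 supplies both the duty and a form. It would be too strong to conclude that such events will go unreported; the defect is a contradicting footnote and a wrong cross-reference.

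**Conclusion.** The point holds and is minor. Two reporting rules contradict each other: for clinically significant Visit 13 laboratory or vital-sign findings, and for related SAEs after Visit 11. Separately, the 28-day figure counts from Visit 9. From the Day 53 (+1) home application the interval is nominally 25 days, range 17 to 32, so for subjects treated to the end collection nominally stops 5 days before the 30-day window closes.

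The number affected is unknown, because the documents give no distribution of last-application dates; subjects whose warts clear earlier have a smaller gap or none. Safety is descriptive and both arms follow the same rules, so no test result changes. The calculation assumes visits and applications within their permitted windows, and Visit 11 attended. Which AE reporting rule was intended cannot be read from the documents; the sections have to be reconciled.

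**What to change.** Choose one of two routes, according to whether data collection is still open. SAP 3.6 records a correction made after unblinding, so it may well have closed.

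- **Collection open.** Record all AEs through the existing Visit 12. Change the Table 2 AE row, footnote 17 (Protocol and SAP) and 14.1.3 together: replace the Visit 11 cut-off and the 28-day clause, and move the related-SAE provision to after Visit 12.
- **Collection closed.** Keep Visit 11. Correct the clause to 28 days from Visit 9 and nominally 25 days from the Day 53 home application. Footnote the AE tables to say that the 30-day window is not fully observed for subjects treated to the end.

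In both cases:

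1. Reconcile 13.2 and 13.3 with footnote 17 and 14.1.3, so that a clinically significant Visit 13 finding has one AE rule. Moving the cut-off to Visit 12 does not do this by itself, because Visit 13 is later still.
2. Add a descriptive table of post-therapy AEs by arm.
3. Reconcile footnote 17 with 14.1.3 on related SAEs after the cut-off, point the cross-reference to 14.1.3 and 14.2.2, and say whether the 14.2.2 procedure applies to those SAEs.

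The cost is a little more AE data entry at Visit 12 (first route only), one extra table and wording changes. No visit or blood draw is added.
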